11.4.3. Urinalysis

Urinalysis includes the following tests: specific gravity, glucose, ketones, blood, pH, and protein, and microscopic analysis. Since urinalysis will only be performed when clinically indicated after screening, the results will only be listed in a listing.

11.4.4. Coagulation

Coagulation includes the following tests: prothrombin time with international normalized ratio and partial thromboplastin time. Since coagulation will only be performed when clinically indicated after screening, the results will only be listed in a listing.

11.4.5. Fasting Lipid Panel

Fasting lipid panel includes total cholesterol, low-density lipoprotein cholesterol (LDL-C), high-density lipoprotein cholesterol (HDL-C), and triglycerides. Lipid profiles will be described by concentration of the lipids at scheduled visits. The proportion of subjects with clinically meaningful post-baseline increase in lipids will be summarized based on criteria presented in Table 6 below.

Table 6: Fasting Lipid Changes of Interest

Laboratory Test	Parameters for any value and the last value
LDL cholesterol	>ULN and >10% increase from BL
LDL-C/HDL-C ratio	>3.5 and >10% increase from BL

11.4.6. Cardiac Markers

Cardiac markers include creatine kinase and cardiac troponins I. Incidence of the test values above upper limit of normal will be summarized at scheduled visits.

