  - Chemistry panel including sodium, potassium, calcium, magnesium, chloride, phosphorus, CO2, bicarbonate, blood urea nitrogen (BUN), creatinine, glucose, albumin, total protein, alkaline phosphatase (ALP), bilirubin (total and direct), uric acid, lactate dehydrogenase (LDH), AST/SGOT, ALT/SGPT, gamma glutamyl transpeptidase (GGT), amylase and lipase
  - UGT1A1 gene mutation test performed on peripheral blood samples for diagnosis of Gilbert's syndrome (refer to the inclusion criterion regarding serum total bilirubin in Section 4.2)
- Assessing AEs [REDACTED] start when the subject signs the ICF
- Transfusion history including the type, number of units, reason, and date of transfusions for the 8 weeks prior to the start of study treatment

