## **6.2. Treatment Phase**

The subject should continue to be eligible for study entry prior to the start of study treatment on Day 1 of Cycle 1. Study Treatment is to be initiated on Day 1 of each treatment cycle. One treatment cycle (one month) is considered as 28 days (ie, 4 weeks). Unless noted otherwise, an administrative window of  $\pm 3$  days is permitted for all subsequent visits after the start of study treatment in the Treatment Phase. Day 1 of Cycles 2 and beyond may be delayed from Day 28 of the prior cycle in order for subjects to recover from toxicity and meet criteria for initiating each treatment cycle (see Section 7.2 for details).

[figure not shown]
The following evaluations will be performed during study treatment at the frequency specified in the Table of Events, Table 3, or more frequently if clinically indicated. The evaluations should be performed prior to dosing on scheduled clinical visit day, unless otherwise specified. For each evaluation, the same parameters as required at screening or on Day 1 of Cycle 1 should be evaluated.

- Registration of the start of each treatment cycle in IVRS (where applicable)

- HRQoL (EORTC QLQ-C30 and EQ-ED-5L questionnaires; Section 6.9)
- Treatment accountability (where applicable; also refer to Section 7.5)
- ECOG performance status
- Physical examination, vital signs and body weight. Significant findings are to be reported on the appropriate eCRF page.
- Body surface area calculation. Where applicable, the dose should be calculated on Day 1 of each treatment cycle.
- The following laboratory assessments will be done locally:
  - ECHO if clinically indicated
  - 12-lead ECG. Abnormal finding(s) will be reported on the appropriate eCRF page.
  - A serum or urine (investigator's discretion under local regulations)  $\beta$ -hCG pregnancy test (sensitivity of at least 25 mIU/mL) is to be done within 72 hours prior to study treatment administration on Day 1 of each treatment cycle (for FCBPs only; note that the central serum pregnancy test at screening can be used as the test prior to the start of study treatment in the Treatment Phase if it is performed within the 72-hour timeframe). The subject may not receive study treatment until the investigator has verified that the result of the pregnancy test is negative.
- The following laboratory assessments will be done centrally:
  - Urinalysis and/or coagulation test if clinically indicated
  - Hematology panel
  - Chemistry panel

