  - Cardiac marker troponin I
  - Fasting (preferred) lipid panel including total cholesterol, low-density lipoprotein cholesterol (LDL-C), high-density lipoprotein cholesterol (HDL-C), triglycerides. Fasting is recommended, particularly for subjects who experience clinically meaningful elevations of lipids, per the investigator's assessment.
- Continuous evaluations of AEs, [REDACTED] concomitant medications and procedures, and transfusions
- Bone marrow aspirate (or biopsy if adequate aspirate is not attainable) samples will be collected for assessing response during study treatment. As specified in the Table of Events, Table 3, the frequency is within 7 days prior to study treatment administration on Cycles 2 and 3, every 2nd cycle thereafter (eg, Cycles 5, 7, 9, etc), and if clinically indicated (eg, confirmation of CR/CRi/CRp, morphologic relapse after CR/CRi/CRp or PD by a repeated bone marrow assessment at least 1 month later) or required for toxicity assessment. A bone marrow biopsy can be collected in

conjunction with an aspirate if it is standard institutional practice or if clinical indicated (eg, evaluation of bone marrow cellularity). Whenever a bone marrow sample is collected, a peripheral blood smear is to be prepared. In addition, whenever a bone marrow aspirate is obtained for confirming CR/CRi/CRp, morphologic relapse after CR/CRi/CRp or PD, a sample of the bone marrow aspirate is to be sent to the local or central cytogenetics laboratory (for sites without local analysis capability) for standard metaphase preparation and analysis of a minimum of 20 metaphase cells. A bone marrow biopsy can be used for cytogenetics testing if adequate aspirate is not attainable (note that specific handling of the biopsy is required for cytogenetics testing). Bone marrow aspirate and/or biopsy, peripheral blood smear and cytogenetics collected after the start of study treatment for response assessment must be available for both local and central review. Instructions for submission slides of bone marrow aspirate (and/or biopsy) and peripheral blood smear, and pertinent reports for central review are provided in the Study Reference and Study Central Laboratory Manuals

- Response to treatment and HI will be assessed whenever bone marrow samples are collected for response assessment (see above)

- Treatment dispensing and administration (where applicable; refer to Section 7)

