### 9.1. Overview

This is an international, multicenter, open-label, randomized, Phase 3 study comparing the efficacy and safety of AG-221 versus CCRs in subjects 60 years or older with AML refractory to or relapsed after second- or third-line AML therapy and positive for an IDH2 mutation.

All data will be summarized by treatment group. In addition, where appropriate, a total column will be included to summarize subjects across treatment groups. Summaries of continuous variables will present the number of subjects included in the analysis (N), the mean and standard deviation (SDev) of the mean, the median, the minimum, and the maximum statistics. Counts and percentages will be presented in summaries of categorical variables. The denominator for each percentage will be the number of subjects in the population treatment group unless otherwise specified. In general, missing data will not be imputed unless otherwise specified.

All statistical analyses specified in this protocol will be conducted using SAS® Version 9.2 or higher unless otherwise specified.

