**The amendment also includes several other minor clarifications and corrections:**

- Medical monitor contact information and Celgene therapeutic head signature page were updated on pages 2 and 3.

- Citations of AG-221 and azacitidine IBs were removed in Section 17 and the links to these citations (in the Protocol Summary, and Sections [redacted] 10.6) were abolished to allow reference to the current IBs.

- Multi-gated acquisition (MUGA) scan was removed as an assessment during screening and/or treatment. However, a prior MUGA scan performed within 28 days prior to the start of study treatment can be used for study entry. These changes were reflected in the Protocol Summary, Table 3, and Sections 6.1, 6.2, and 6.4.
- The window for bone marrow aspirate and/or biopsy, peripheral blood smear and, if applicable, cytogenetics, during the Treatment Phase was clarified in the footnotes “w”, “x” and “y” of Table 3 to be consistent with Section 6.2.
- The window for bone marrow aspirate and/or biopsy, peripheral blood smear and, if applicable, cytogenetics, during the Follow-up Phase was corrected in Section 6.3 to  $\pm 14$  days to be consistent with the footnote “q” of the Protocol, Table 3, Table of Events.
- The parameters of chemistry and cardiac marker panels were updated.
- Truncated sentences in Sections 8.1 and 10.6 were completed.
- The elapsed time from azacitidine reconstitution to administration in Method A of Appendix K was updated with addition of the specification in the United States.
- Specification of azacitidine reconstitution with refrigerated water was added in Method B of Appendix K.
- Corrections of minor typographical errors and incidental formatting changes were made throughout the document.

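### SAP 11.4.6 tabulates cardiac markers above ULN only at scheduled visits, with no any-time count, baseline condition or stated denominator, so new troponin I elevation cannot be identified

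*SAP*

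**What the plan says.** SAP 11.4.6 consists of two sentences. The first names the analytes: "Cardiac markers include creatine kinase and cardiac troponins I". The second is the whole analysis: "Incidence of the test values above upper limit of normal will be summarized at scheduled visits".

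The surrounding text bears on how that would be programmed:

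- **Record selection (SAP 11.4).** Where several laboratory records belong to one visit, the record nearest in time is used, not the worst.
- **Testing off schedule (Protocol 6.2).** Evaluations follow Table 3 "or more frequently if clinically indicated".
- **Denominator (Protocol 9.1).** "The denominator for each percentage will be the number of subjects in the population treatment group unless otherwise specified". Neither SAP 5.1 nor SAP 11.4.6 specifies otherwise for this table.
- **Neighbouring tables.** Tables 5 (serum chemistry) and 6 (lipids) are headed "Parameters for any value and the last value", and the Table 6 criteria also require an increase from baseline.
- **Analytes collected.** Protocol 6.2 lists "Cardiac marker troponin I" and no other cardiac marker. The chemistry panel in Protocol 6.1, which ends with "gamma glutamyl transpeptidase (GGT), amylase and lipase", does not contain creatine kinase. The protocol's amendment summary records that "The parameters of chemistry and cardiac marker panels were updated", without naming analytes. SAP 13 lists no change concerning cardiac markers.

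**The concern.** A safety reader wants to know from this table what proportion of subjects in each arm developed a troponin I elevation on treatment. The planned summary does not give that proportion, for three reasons.

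1. A value drawn between visits, for instance on clinical suspicion, is used only if it is the record nearest a scheduled visit. Otherwise it does not reach the between-arm table.
2. Without a baseline condition, a subject already above ULN on Cycle 1 Day 1 is counted in the same way as a new case. No exclusion criterion in Protocol 4.3 names troponin, so such subjects can be enrolled.
3. With no denominator stated, a programmer may fall back on the whole arm. A subject no longer tested then counts as not elevated, and the percentage partly reflects time on treatment.

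Separately, a creatine kinase row would have few or no data under the current panel, with nothing to tell the reader why.

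**Working it through.** The documents give no figure for cardiac markers, so there is none to reproduce. The elevation rates, baseline shares and treatment-time medians below are assumptions. The documents supply only the 28-day cycle, the 30.4375-day month and the OS medians of 8 months (AG-221) and 5.6 months (CCR) from SAP 4.4. Survival bounds time on treatment, so the OS medians serve as a ceiling.

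**1. Whole-arm denominator.** Share still on treatment at Day 1 of cycle c = exp(−ln 2 × t / median), with t = (c − 1) × 28 / 30.4375 months. At Cycle 6, t = 140 / 30.4375 = 4.60 months.

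- AG-221: exp(−ln 2 × 4.60 / 8) = 0.671
- CCR: exp(−ln 2 × 4.60 / 5.6) = 0.566

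With 10% of tested subjects above ULN in both arms, the table percentage is 10% × share:

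| Treatment-time medians (AG-221 / CCR, months) | Cycle 6 | Ratio | Cycle 9 | Ratio |
|---|---|---|---|---|
| 8 / 5.6 (OS ceiling) | 6.7% vs 5.7% | 1.19 | 5.3% vs 4.0% | 1.31 |
| 4 / 2.8 (half of OS) | 4.5% vs 3.2% | 1.41 | 2.8% vs 1.6% | 1.73 |
| 4 / 4 (equal) | 4.5% vs 4.5% | 1.00 | 2.8% vs 2.8% | 1.00 |

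With subjects tested at the visit as denominator, every cell is 10% versus 10%.

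**2. Missing baseline condition.** Let b be the share already above ULN at baseline and remaining so, and e the rate of new elevation among the rest. The table then shows b + (1 − b)e of tested subjects. For e = 5%:

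- b = 5%: 0.05 + 0.95 × 0.05 = 9.75%
- b = 10%: 0.10 + 0.90 × 0.05 = 14.5%
- b = 20%: 0.20 + 0.80 × 0.05 = 24%

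**3. Both together at Cycle 6.** Multiply by 0.566 (CCR) and 0.671 (AG-221), against a true new rate of 5%:

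- b = 0: 2.8% and 3.4% (too low)
- b = 5%: 5.5% and 6.5% (slightly high)
- b = 10%: 8.2% and 9.7% (too high)

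The sign of the error therefore depends on baseline prevalence, which is unknown.

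**4. Off-schedule values.** Routine sampling appears to be every third cycle, or 3 × 28 = 84 days. This rests on a Table 3 footnote whose link to the cardiac row was lost in extraction; it is inferred from the matching 14-day exemption at EOT in Protocol 6.2.3. At that spacing a scheduled sample meets an elevation lasting 7, 14 or 28 days with probability 7/84 = 8%, 14/84 = 17% or 28/84 = 33%. Most of that gap belongs to the sampling schedule. The SAP rule adds only the loss of elevations that were measured off schedule and then not tabulated.

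**The case against.** The strongest reply is that the information is not lost. Protocol 10.3 makes a laboratory abnormality an adverse event if it needs treatment or a dose change or is of significant clinical importance, and SAP 11.1 tabulates TEAEs through the treatment period, including per person-year. SAP 11.4 promises change from baseline for laboratory results in general, a shift to worst grade where data allow, listings of all central values with abnormal flags, and listings of local values. EOT is itself a cardiac marker visit unless one was done in the preceding 14 days. An unscheduled sample can also enter a visit if it is the nearest record. All of this stands, and it limits the harm. None of it gives the proportion of subjects newly above ULN by arm, and grade shifts are specified again only for hematology and serum chemistry.

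The denominator point is an inference. SAP 11.4.6 does not state a whole-arm denominator, and its sentence can also be read as values above ULN among values obtained at that visit. That stands too: the dilution is conditional on the default being applied.

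Nor is the lack of a baseline condition peculiar to cardiac markers, since the ALT, AST and bilirubin rows of Table 5 have none either. Those rows do, however, count any value.

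Finally, an any-time count is not free of exposure. Assuming 5% new elevation per independent test, one test gives 5% and three give 1 − 0.95³ = 14.3%, a 2.9-fold gap with equal risk. This stands, and the fix must allow for it.

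**Conclusion.** The point holds as a cheap improvement to one descriptive safety table; no hypothesis test or decision rule depends on it. As specified, the table can omit elevations measured off schedule and cannot separate new from existing troponin I elevation. If the whole-arm default is used, it also varies with time on treatment: about 1.2-fold between arms at Cycle 6 under the OS ceiling, 1.4-fold if treatment medians are half of that, and nothing if treatment time is equal.

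Three stronger readings are tempting, and the documents do not support them.

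- A reader might infer that the table understates elevations. The missing baseline condition works the other way, and the net direction is not fixed.
- A reader might infer a large false difference between arms. Treatment medians of 5 and 2 months would give 5.3% versus 2.0% at Cycle 6, a ratio of 2.6, but neither document states a median time on treatment.
- A reader might infer that creatine kinase is simply an error to strike out. The panel was updated by amendment and the analytes are not named, so subjects enrolled earlier may have creatine kinase results. The mismatch leaves at worst an empty or partial row and does not bias the troponin I figures.

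**What to change.** In SAP 11.4.6:

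1. Report the number and percentage of subjects with any post-baseline troponin I above ULN in the treatment period, counting scheduled, unscheduled and EOT samples, among subjects at or below ULN at baseline with at least one post-baseline value.
2. Show subjects elevated at baseline in a separate row.
3. Add the last value, as in Tables 5 and 6.
4. Add an exposure-adjusted rate, because the any-time count rises with time on treatment.
5. If by-visit percentages are kept, use subjects tested at that visit as the denominator and print that number.
6. Reconcile creatine kinase with the current protocol panel. Keep any results already collected and show the number tested.

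One detail needs settling when the baseline condition is written. SAP 5.1 takes baseline for BSC-only subjects on or before randomization, whereas the screening list in Protocol 6.1 contains no cardiac marker. A BSC-only subject first sampled after the randomization date would have no baseline value, so the SAP should say how such subjects are handled.

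The cost is SAP wording, one reprogrammed table and an extra row. No new data collection is needed.

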11.4.7. Females of Childbearing Potential

Pregnancy incidences will be reported as adverse events and listed out at subject level.

11.5. Vital Sign Measurements

Evaluation of vital signs includes recording height (only at screening), weight, temperature, systolic blood pressure (SBP), diastolic blood pressure (DBP), pulse rate, and respiratory rate at scheduled visits.

Vital sign measurements will be listed for each subject and by scheduled visit. Descriptive statistics for vital signs (except height), both observed values and changes from baseline, will be summarized by treatment group.

11.6. Physical Examination

Abnormal physical examination findings will be captured as medical history (screening) and will be summarized as medical history or be captured as adverse events and will be summarized as adverse events.

11.7. Electrocardiograms

Electrocardiogram (ECG) parameters include heart rate, PR interval, QRS duration, RR interval, QT, QTc Fridericia value (QTcF) and QTc Bazett value (QTcB). QTcB is not recorded in the CRF page and will be calculated in the following way: $QTcB = QT / \sqrt{RR}$.

Recorded values and of ECG parameters and change from baseline values will be summarized at each time point by treatment group.

In addition, at baseline and maximum post-baseline visits, the proportion of subjects having absolute QTcF and QTcB intervals of the following categories will be presented:

- ≤ 450 ms
- > 450 to ≤ 500 ms
- > 500 ms

At maximum post-baseline visits, the proportion of subjects who have an increase from baseline in QTcF and QTcB intervals of the following categories will be presented:

- ≤ 30 ms
- > 30 to ≤ 60 ms
- > 60 ms

The overall ECG interpretation will be summarized by presenting the shift from baseline to worst by treatment group and by cycle. The overall ECG interpretation will be displayed in cross-tabulations for each treatment.

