- Documentation of the CCR treatment option selected by the investigator prior to randomization
- ECOG performance status
- Physical examination: information about the screening physical examination must be present in the subject's source documentation. Significant findings must be included on the appropriate eCRF page.
- Vital signs including temperature, blood pressure, pulse rate and respiratory rate

- Height (only collected once at screening)
- Body weight
- Body surface area (BSA) calculation per the Dubois & Dubois formula:  
$$\text{BSA (m}^2\text{)} = \text{weight (kg)}^{0.425} \times \text{height (cm)}^{0.725} / 139.2$$
- The following laboratory assessments will be done locally:
  - ECHO (not required if a prior ECHO or MUGA scan has been performed within 28 days prior to the start of study treatment)
  - 12-lead ECG will be assessed by a physician trained in ECG interpretation as normal, abnormal - not clinically significant, or abnormal - clinically significant. Intervals including PR, QRS, QT and RR will be collected, as well as heart rate and rhythm. Abnormal finding(s) will be reported on the appropriate eCRF page. For a given subject, ECG interpretations should be conducted by the same physician throughout the study as much as possible, with a consistent approach for the QT interval analysis (eg, pre-cordial leads and lead II).
- The following laboratory assessments will be done centrally:
  - Serum  $\beta$ -hCG pregnancy test (sensitivity of at least 25 mIU/mL) is required for all FCBPs (see Section 4.2 for the definition)
  - Urinalysis including examination by a standard dipstick test for specific gravity, glucose, ketones, blood, pH, and protein, and microscopic analysis if indicated
  - Coagulation test including prothrombin time (PT) with international normalized ratio (INR) and partial thromboplastin time (PTT)
  - Hematology panel including complete blood count (CBC) with differential, including red blood cell (RBC) count, hemoglobin, hematocrit, mean corpuscular volume (MCV), mean corpuscular hemoglobin (MCH), mean corpuscular hemoglobin concentration (MCHC), white blood cell (WBC) count (with differential), absolute neutrophil count (ANC) and platelet count

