#### **QT Prolongation**

Subjects who experience prolongation of the heart rate-corrected QT interval, Fridericia's correction (QTcF) to  $> 480$  msec (Grade  $\geq 2$ ) while treated with AG-221, should be promptly evaluated for causality of the QTc prolongation and managed according to the following guidelines:

- Levels of electrolytes (potassium, calcium and magnesium) should be checked and supplementation given to correct any values outside the normal range.
- Concomitant therapies should be reviewed and adjusted as appropriate for medication with known QT prolonging effects.
- If no other cause is identified and the investigator believes it is appropriate, particularly if QTc remains elevated (after above measures have been implemented, or as determined by the investigator), AG-221 treatment may be interrupted, and an

ECG should be rechecked in approximately 1 week after the QTc prolongation was first observed or more frequently as clinically indicated.

- If QTc has recovered or improved and the investigator believes it is safe to do so, a re-challenge with AG-221 should be considered if held. ECGs should be conducted at least weekly (eg, at every scheduled visit) for 2 weeks following QTc reduction  $\leq 480$  msec.
- If Grade 2 (QTcF  $> 480$  and  $\leq 500$  msec), the dose of AG-221 may be reduced without interruption of dosing. The AG-221 dose may be re-escalated to the prior dose in  $\geq 14$  days after QT prolongation has decreased to  $\leq$  Grade 1.
  - If this is the second occurrence of QT prolongation, administration of AG-221 should continue at a reduced dose (ie, the dose may not be re-escalated).
- If Grade 3 (QTcF  $> 500$  msec), hospitalization for continuous cardiac monitoring and evaluation by a cardiologist should both be considered. Dosing with AG-221 will be interrupted. If QTc returns to within 30 msec of baseline or  $< 450$  msec within 14 days, treatment may be resumed at a reduced dose. The AG-221 dose cannot be re-escalated following dose reduction for Grade 3 QTcF prolongation unless the prolongation was associated with an electrolyte abnormality or concomitant medication.

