## 9.7. Safety Analysis

All safety analyses will be performed on the safety population.

Adverse events will be summarized by the Medical Dictionary for Regulatory Activities (MedDRA) system organ class and preferred term. Treatment-emergent AEs leading to death, TEAEs leading to discontinuation from treatment, CTCAE Grade 3 or Grade 4 TEAEs, TEAEs any CTCAE grade, TEAEs related to study treatment and serious TEAEs will be summarized separately.

Clinical laboratory results will be listed and summarized descriptively by treatment group, which will also include a display of change from baseline. Laboratory values outside of the normal ranges will be identified. Clinically significant hematologic and nonhematologic laboratory abnormalities that meet Grade 3 or Grade 4 criteria according to the CTCAE will be listed and summarized. Graphical display of select laboratory parameters over the course of the study will be provided where useful to assist in the interpretation of results.

Vital sign measurements will be listed for each subject at each visit collected. Descriptive statistics for vital signs, both observed values and changes from baseline, will be summarized by treatment group.

Electrocardiograms will be analyzed for QTc intervals, QTc > 480 and > 500, increase > 30 and > 60 msec.

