13. CHANGES TO THE STATISTICAL ANALYSES SECTION OF THE PROTOCOL

Additional analysis of the Transfusion Independence of subjects will be conducted, which is not mentioned in the Protocol. For details see Section [10.3.2.8](#) of this SAP.

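### SAP 11.7 has no 480 ms cut-point, so the protocol's analysis of QTc above 480 ms is not planned and cannot be read from the SAP table

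*SAP*

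**What the plan says.** Protocol 9.7 (Safety Analysis) sets out the ECG analysis in one sentence: "Electrocardiograms will be analyzed for QTc intervals, QTc > 480 and > 500, increase > 30 and > 60 msec". That is two absolute thresholds and two change thresholds.

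Protocol 7.2.1.3 (QT Prolongation) gives 480 msec a role in the conduct of the trial. Subjects on AG-221 whose QTcF rises above 480 msec (Grade 2 or higher) "should be promptly evaluated for causality of the QTc prolongation and managed according to the following guidelines". The same section defines Grade 2 as QTcF above 480 and up to 500 msec.

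SAP 11.7 (Electrocardiograms) states that at baseline and at the maximum post-baseline visit "the proportion of subjects having absolute QTcF and QTcB intervals of the following categories will be presented". There are three categories: ≤ 450 ms, "> 450 to ≤ 500 ms", and > 500 ms. Increases from baseline are cut at 30 and 60 ms. The section also plans descriptive summaries ("Recorded values and of ECG parameters and change from baseline values will be summarized at each time point by treatment group") and shifts in the overall ECG interpretation.

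SAP Section 13, which records changes to the protocol's analyses, has one entry: "Additional analysis of the Transfusion Independence of subjects will be conducted, which is not mentioned in the Protocol".

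**The concern.** The SAP is the document from which the tables will be programmed. Followed as written, it leaves out an analysis the protocol specifies, without saying so, and at the level where the protocol's own QT guidance starts to apply. QT prolongation is also the first adverse event of special interest listed in SAP 11.2.

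What is at stake is a by-arm count of subjects whose measured QTc exceeded 480 ms. The trial is open-label, and investigators decide what to report as an adverse event. A count of measured values gives a comparison between arms that does not depend on that decision. With a single band from 450 to 500 ms, a reader of the study report could not tell how many subjects in either arm passed 480 ms.

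**Working it through.** No sample size, power or alpha is involved. The check is which threshold counts can be formed by adding SAP categories.

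**Inputs.** Protocol thresholds from Protocol 9.7: absolute > 480 and > 500 msec; increase > 30 and > 60 msec. SAP cut-points from SAP 11.7: absolute 450 and 500 ms; increase 30 and 60 ms.

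**Step 1. Match thresholds to cut-points.** A count above x can be formed only if x is a cut-point.

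| Protocol threshold | SAP cut-point? | Obtainable from SAP table? |
|---|---|---|
| QTc > 480 | No (inside > 450 to ≤ 500) | No |
| QTc > 500 | Yes | Yes |
| Increase > 30 | Yes | Yes (sum of top two bands) |
| Increase > 60 | Yes | Yes |

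One of the two absolute thresholds and both change thresholds can be obtained: three of four in all.

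**Step 2. What the SAP table does say about > 480.** Let *b* be the number of subjects in > 450 to ≤ 500 and *c* the number in > 500. Then

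*c* ≤ N(> 480) ≤ *b* + *c*.

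The uncertainty equals *b*, the whole of the middle band. The documents give no figure for *b*, so no numerical width can be stated.

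**Step 3. Look for the count elsewhere in the SAP.**

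- SAP 11.7, summaries by time point: descriptive statistics of values and changes. Under SAP 5.1 these include the maximum, so a value above 480 ms at a summarised visit might be visible, but subjects are not counted.
- SAP 11.7, overall interpretation shift: uses the reader's interpretation, not a QTc threshold.
- SAP 11.4, CTCAE grading: laboratory tests only.
- SAP 11.2, QT special interest: a standardised MedDRA query on reported adverse events. Its severity summary is Grade 3 or higher.
- SAP 11.1, events by maximum severity: could show Grade 2 events, but only those reported as adverse events.

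None counts measured QTc above 480 ms.

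**Step 4. Check for a declared change.** The only entry in SAP Section 13 is transfusion independence. No ECG change is recorded.

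**Step 5. Check the repair.** With bands ≤ 450, > 450 to ≤ 480, > 480 to ≤ 500 and > 500 ms, N(> 480) is the sum of the last two bands, N(> 500) is the last band, and the existing > 450 count is the sum of the last three. All four protocol thresholds are then available and nothing now planned is lost.

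**The case against.** The best defence is that Protocol Section 9 calls itself an overview and leaves the detailed methods to the SAP, so the SAP may choose its own categories. The remaining ECG and adverse-event outputs are also substantial: > 500 ms, both change thresholds, values by visit and arm, the QT query with serious, related and Grade 3 or higher tables, and events leading to dose reduction or interruption. Both points stand in part. The SAP may depart from the protocol, but a departure belongs in Section 13. The other outputs mean that QT safety is far from unreported, but none of them supplies this count.

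Four stronger readings are tempting and are not supported.

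- *The count is impossible to produce.* It is not. Protocol 6.1 provides that "Intervals including PR, QRS, QT and RR will be collected, as well as heart rate and rhythm", and QTcF is among the SAP's ECG parameters. The count can be derived per subject; it is simply not planned.
- *Everyone enters below 450 ms, so every value in the middle band is a new rise.* Exclusion criterion 19 applies to QTcF at screening only. The ECG is repeated on Day 1, the SAP baseline can be a Day 1 value, and QTcB has no entry limit. The post-baseline table also classifies one maximum per subject, so someone with 490 ms and later 510 ms appears only in > 500.
- *Grade 2 is pooled with Grade 1.* The documents define Grade 2 but give no lower bound for Grade 1. What can be said is that values at or below 480 ms are merged with the Grade 2 range.
- *The protocol demands the 480 ms cut for QTcB as well.* Protocol 9.7 says only QTc, and the 480 msec level in 7.2.1.3 is for QTcF in subjects on AG-221. Splitting QTcB is a matter of consistency.

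**Conclusion.** The point holds as a mismatch between the protocol and the SAP in safety reporting. The analysis of QTc above 480 ms is specified in Protocol 9.7, absent from SAP 11.7, not recoverable from the planned categories, not supplied by another output, and not declared as dropped. Its size is one of four ECG thresholds, with the missing count known only to within the size of the middle band.

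The conclusion assumes that Protocol 9.7 means counts or proportions of subjects above each threshold, which is how SAP 11.7 treats the other three. Any other reading of that sentence would still need a cut at 480 ms. It also assumes that no ECG table outside the SAP text supplies the count. Primary and key secondary inference is unaffected, and nothing here bears on whether 480 msec is the right clinical action level.

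**What to change.** In SAP 11.7, replace the middle absolute category by two, > 450 to ≤ 480 ms and > 480 to ≤ 500 ms, for QTcF at minimum and for QTcB for consistency, at baseline and at the post-baseline maximum. A cumulative line for > 480 ms would let the protocol's figure be read directly.

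If the sponsor prefers to keep the three bands, Section 13 should state that the > 480 ms analysis in Protocol 9.7 is dropped, and why.

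The split adds one row per table (a cumulative line would add another) and a small programming change. It needs no new data and no change to trial conduct, and it should be made before the database lock for the final analysis.
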